9.18.2 Pediatric Outcome Data Collection Instrument

The questionnaire to document health related quality of life is the PODCI. The Pediatric Outcomes Questionnaire is designed to be completed by the parent/guardian of the children aged 10 years old or younger. The Adolescent (parent-reported) Outcomes Questionnaire is designed to be completed by the parent/guardian for adolescents aged 11 to 18 years old, and the Adolescent (self-reported) Outcomes Questionnaire is designed to be completed by adolescents aged 11 to 18 years old. Patients should not switch questionnaires during the study based upon an age change. Please refer to the SRM for further details on how to administer the PODCI questionnaire.

9.18.3 Personal Adjustment and Role Skills Scale, 3rd Edition Questionnaire

PARS III is a questionnaire designed for DMD young men that asks parents/guardians about their child's well-being and psychosocial adjustment ([Hendriksen et al, 2009](#)). Please refer to the SRM for further details on how to administer the PARS III Questionnaire.

9.18.4 Other Assessments

9.18.4.1 Actigraphy (ActiGraph GT9x)

During the Screening process and prior to baseline assessments, patients will be provided with an ActiGraph GT9x, specific information regarding the device, and the wear protocol. Patients will wear the ActiGraph on their non-dominant wrist throughout the study period (10 hour daytime + full nighttime wear). Daily bouts of activity (energy expenditure) and percent sleep efficiency, nighttime awakenings, and duration of nighttime awakenings will be explored through the ActiLife data analyses software platform. Sleep-wake activity analyses will be performed using R*Studio and nparACT software to compute several non-parametric measures from raw actigraphy data. Specifically, the interdaily stability, intradaily variability, and relative amplitude of activity will be computed to explore sleep-wake activity rhythms (circadian rhythmicity) in study patients.

9.18.5 Respiratory Assessments

9.18.5.1 Peak Expiratory Flow

PEF is a measure of the maximal flow rate that can be achieved during forceful expiration following full inspiration.

PEF rate will be calculated based on the patient's age, height, and race/ethnicity.

9.18.5.2 Forced Vital Capacity

FVC is the maximum amount of air exhaled by a patient after a maximal inhalation.

9.18.5.3 Forced Expiratory Volume in 1 Second

FEV1 is the amount of air forcefully exhaled by the patient in the first second after full inspiration.

9.18.5.4 Peak Cough Flow

PCF will be measured using a peak flow meter. The test will be performed by asking the patient to inspire completely until total lung capacity and subsequently cough forcefully. During the test, patients breathe through a mouthpiece while wearing noseclips or a face mask linked to a peak flow meter or to a pneumotachograph.

9.18.6 Chest X-ray

The chest X-ray will include images of the heart, lungs, airways, blood vessels, and the bones of the spine and chest.

10 STUDY ACTIVITIES

10.1 Pretreatment Phase

The Pretreatment Phase will be comprised of a minimum of 2 visits: a Screening Visit to allow the investigator to assess the patient's eligibility and a Pre-Infusion Visit. The SRM provides details on order of testing and data collection information.

10.1.1 Screening Visit (-28 to -8 Days)

The ICF/Assent Form must be obtained prior to any study-related procedures being conducted. Screening will include assessments to confirm eligibility (review of inclusion/exclusion criteria and review to confirm the DMD diagnosis and appropriate mutations).

Screening activities:

- Informed consent/assent
- Review of inclusion/exclusion criteria
- Confirm DMD diagnosis
- DMD genetic test
- Demographics
- Medical history
- Height and weight
- Vital signs
- Physical and neurological examination
- 12-lead ECG
- Renal ultrasound
- Echocardiogram
- Antigen and antibody testing: hepatitis B antigen, hepatitis C virus antibody, and HIV antibody
- Hematology
- Chemistry
- Urinalysis (random urine)

- Respiratory assessments
 - FVC
 - FEV1
 - PEF
 - PCF
- Function and strength
 - NSAA
 - Vignos scale
 - Hand-held dynamometer
 - Brooke scale
 - PUL
- Patient reported outcomes
 - PODCI
 - PARS III Questionnaire
- AE review
- Provision of the ActiGraph GT9x and wear protocol

10.1.2 Pre-Infusion Visit (-7 to -1 Days)

The following assessments will occur:

- Review of inclusion/exclusion criteria
- Medical history (any updates will be recorded)
- Height and weight
- Vital signs
- Physical and neurological examination
- First morning void urinalysis

Note: Analysis of the first morning void urine sample will include urine dipstick protein to be performed at the site.

- Urine cytology (utilizing a urine sample collected on-site)

- Respiratory assessments
 - FVC
 - FEV1
 - PEF
 - PCF
- Function and strength
 - NSAA
 - Vignos scale
 - Hand-held dynamometer
 - Brooke scale
 - PUL
- Patient reported outcomes
 - PODCI
 - PARS III Questionnaire
- Chest X-ray
- AE review
- Ensure wearing of the ActiGraph GT9x

10.2 Treatment Phase

If allowed per local regulations, Weeks 6 to 8, 10 to 12, 14 to 16, 18 to 20, 22 to 24, 26 to 36, and 38 to 47 can be completed at a non-site location via the home health vendor. NS Pharma, Inc. reserves the right to require visits to be completed at the site, if needed.

10.2.1 Day 1 Dosing Visit (First Infusion)

The following assessments will occur:

- Medical history (any updates will be recorded)
- Height and weight
- Vital signs (predose, 1 hour [up to 20 minutes following completion of the infusion] and 2 hours [\pm 20 minutes] after initiation of infusion)
- Physical and neurological examination
- 12-lead ECG

- Hematology
- Chemistry
- Postdose urinalysis (utilizing a urine sample collected within 5 hours after completion of the infusion)
- Anti-dystrophin antibody (predose)
- Anti-viltolarsen antibody (predose)
- PK blood sample (predose [within 60 minutes prior to infusion] and 2 hours [\pm 20 minutes] after initiation of infusion)
- IP administration
- Respiratory assessments
 - FVC
 - FEV1
 - PEF
 - PCF
- AE review
- Data upload from ActiGraph GT9x

10.2.2 Week 2

The following assessments will occur:

- Medical history (any updates will be recorded)
- Vital signs (predose, 1 hour [up to 20 minutes following completion of the infusion] and 2 hours [\pm 20 minutes] after initiation of infusion)
- IP administration
- AE review
- Data upload from ActiGraph GT9x

10.2.3 Week 3

The following assessments will occur:

- Medical history (any updates will be recorded)

- Vital signs (predose, 1 hour [up to 20 minutes following completion of the infusion] and 2 hours [\pm 20 minutes] after initiation of infusion)
- Hematology
- Chemistry
- First morning void urinalysis

Note: Analysis of the first morning void urine sample will include urine dipstick protein to be performed at the site.

- IP administration
- AE review
- Data upload from ActiGraph GT9x

10.2.4 Week 4

The following assessments will occur:

- Medical history (any updates will be recorded)
- Vital signs (predose, 1 hour [up to 20 minutes following completion of the infusion] and 2 hours [\pm 20 minutes] after initiation of infusion)
- IP administration
- AE review
- Data upload from ActiGraph GT9x

10.2.5 Week 5

The following assessments will occur:

- Medical history (any updates will be recorded)
- Vital signs (predose, 1 hour [up to 20 minutes following completion of the infusion] and 2 hours [\pm 20 minutes] after initiation of infusion)
- Physical and neurological examination
- Hematology
- Chemistry

- First morning void urinalysis

Note: Analysis of the first morning void urine sample will include urine dipstick protein to be performed at the site.

- IP administration
- AE review
- Data upload from ActiGraph GT9x

10.2.6 Weeks 6 to 8

The following assessments will occur:

- Medical history (any updates will be recorded)
- Vital signs (predose, 1 hour [up to 20 minutes following completion of the infusion] and 2 hours [\pm 20 minutes] after initiation of infusion)
- IP administration
- AE review
- Data upload from ActiGraph GT9x

10.2.7 Week 9

The following assessments will occur:

- Medical history (any updates will be recorded)
 - Vital signs (predose, 1 hour [up to 20 minutes following completion of the infusion] and 2 hours [\pm 20 minutes] after initiation of infusion)
 - Physical and neurological examination
 - Hematology
 - Chemistry
 - First morning void urinalysis
- Note: Analysis of the first morning void urine sample will include urine dipstick protein to be performed at the site.
- IP administration
 - AE review
 - Data upload from ActiGraph GT9x

10.2.8 Weeks 10 to 12

The following assessments will occur:

- Medical history (any updates will be recorded)
- Vital signs (predose, 1 hour [up to 20 minutes following completion of the infusion] and 2 hours [\pm 20 minutes] after initiation of infusion)
- IP administration
- AE review
- Data upload from ActiGraph GT9x

10.2.9 Week 13

The following assessments will occur:

- Medical history (any updates will be recorded)
- Height and weight
- Vital signs (predose, 1 hour [up to 20 minutes following completion of the infusion] and 2 hours [\pm 20 minutes] after initiation of infusion)
- Physical and neurological examination
- 12-lead ECG
- Hematology
- Chemistry
- First morning void urinalysis

Note: Analysis of the first morning void urine sample will include urine dipstick protein to be performed at the site.

- Urine cytology (utilizing a predose urine sample collected on-site)
- Postdose urinalysis (utilizing a urine sample collected within 5 hours after completion of the infusion)
- Anti-dystrophin antibody (predose)
- Anti-viltolarsen antibody (predose)
- PK blood sample (predose [within 60 minutes prior to infusion] and 2 hours [\pm 20 minutes] after initiation of infusion)

- Respiratory assessments
 - FVC
 - FEV1
 - PEF
 - PCF
- Function and strength
 - NSAA
 - Vignos scale
 - Hand-held dynamometer
 - Brooke scale
 - PUL
- Patient reported outcomes
 - PODCI
 - PARS III Questionnaire
- IP administration
- AE review
- Data upload from ActiGraph GT9x

10.2.10 Weeks 14 to 16

The following assessments will occur:

- Medical history (any updates will be recorded)
- Vital signs (predose, 1 hour [up to 20 minutes following completion of the infusion] and 2 hours [\pm 20 minutes] after initiation of infusion)
- IP administration
- AE review
- Data upload from ActiGraph GT9x

10.2.11 Week 17

The following assessments will occur:

- Medical history (any updates will be recorded)
- Vital signs (predose, 1 hour [up to 20 minutes following completion of the infusion] and 2 hours [\pm 20 minutes] after initiation of infusion)
- Physical and neurological examination
- Hematology
- Chemistry
- First morning void urinalysis

Note: Analysis of the first morning void urine sample will include urine dipstick protein to be performed at the site.

- IP administration
- AE review
- Data upload from ActiGraph GT9x

10.2.12 Weeks 18 to 20

The following assessments will occur:

- Medical history (any updates will be recorded)
- Vital signs (predose, 1 hour [up to 20 minutes following completion of the infusion] and 2 hours [\pm 20 minutes] after initiation of infusion)
- IP administration
- AE review
- Data upload from ActiGraph GT9x

10.2.13 Week 21

The following assessments will occur:

- Medical history (any updates will be recorded)
- Vital signs (predose, 1 hour [up to 20 minutes following completion of the infusion] and 2 hours [\pm 20 minutes] after initiation of infusion)
- Physical and neurological examination

- Hematology
- Chemistry
- First morning void urinalysis

Note: Analysis of the first morning void urine sample will include urine dipstick protein to be performed at the site.

- IP administration
- AE review
- Data upload from ActiGraph GT9x

10.2.14 Weeks 22 to 24

The following assessments will occur:

- Medical history (any updates will be recorded)
- Vital signs (predose, 1 hour [up to 20 minutes following completion of the infusion] and 2 hours [\pm 20 minutes] after initiation of infusion)
- IP administration
- AE review
- Data upload from ActiGraph GT9x

10.2.15 Week 25

The following assessments will occur:

- Medical history (any updates will be recorded)
- Height and weight
- Vital signs (predose, 1 hour [up to 20 minutes following completion of the infusion] and 2 hours [\pm 20 minutes] after initiation of infusion)
- Physical and neurological examination
- 12-lead ECG
- Renal ultrasound
- Echocardiogram
- Hematology
- Chemistry

- First morning void urinalysis
Note: Analysis of the first morning void urine sample will include urine dipstick protein to be performed at the site.
- Urine cytology (utilizing a predose urine sample collected on-site)
- Postdose urinalysis (utilizing a urine sample collected within 5 hours after completion of the infusion)
- Anti-dystrophin antibody (predose)
- Anti-viltolarsen antibody (predose)
- PK blood sample (predose [within 60 minutes prior to infusion] and 2 hours [\pm 20 minutes] after initiation of infusion)
- Respiratory assessments
 - FVC
 - FEV1
 - PEF
 - PCF
- Function and strength
 - NSAA
 - Vignos scale
 - Hand-held dynamometer
 - Brooke scale
 - PUL
- Patient reported outcomes
 - TSQM
 - PODCI
 - PARS III Questionnaire
- IP administration
- AE review
- Data upload from ActiGraph GT9x

10.2.16 Weeks 26 to 36

The following assessments will occur:

- Medical history (any updates will be recorded)
- Vital signs (predose, 1 hour [up to 20 minutes following completion of the infusion] and 2 hours [\pm 20 minutes] after initiation of infusion)
- First morning void urinalysis (Week 29 and Week 33 only)

Note: Analysis of the first morning void urine sample will include urine dipstick protein to be performed at the site.

- IP administration
- AE review
- Data upload from ActiGraph GT9x

10.2.17 Week 37

The following assessments will occur:

- Medical history (any updates will be recorded)
- Height and weight
- Vital signs (predose, 1 hour [up to 20 minutes following completion of the infusion] and 2 hours [\pm 20 minutes] after initiation of infusion)
- Physical and neurological examination
- 12-lead ECG
- Hematology
- Chemistry
- First morning void urinalysis

Note: Analysis of the first morning void urine sample will include urine dipstick protein to be performed at the site.

- Urine cytology (utilizing a predose urine sample collected on-site)
- Postdose urinalysis (utilizing a urine sample collected within 5 hours after completion of the infusion)
- Anti-dystrophin antibody (predose)
- Anti-viltolarsen antibody (predose)

- PK blood sample (predose [within 60 minutes prior to infusion] and 2 hours [\pm 20 minutes] after initiation of infusion)
- Respiratory assessments
 - FVC
 - FEV1
 - PEF
 - PCF
- Function and strength
 - NSAA
 - Vignos scale
 - Hand-held dynamometer
 - Brooke scale
 - PUL
- Patient reported outcomes
 - PODCI
 - PARS III Questionnaire
- IP administration
- AE review
- Data upload from ActiGraph GT9x

10.2.18 Weeks 38 to 47

The following assessments will occur:

- Medical history (any updates will be recorded)
- Vital signs (predose, 1 hour [up to 20 minutes following completion of the infusion] and 2 hours [\pm 20 minutes] after initiation of infusion)
- First morning void urinalysis (Week 41 and Week 45 only)
Note: Analysis of the first morning void urine sample will include urine dipstick protein to be performed at the site.
- IP administration

- AE review
- Data upload from ActiGraph GT9x

10.2.19 Week 48

The following assessments will occur:

- Medical history (any updates will be recorded)
- Vital signs (predose, 1 hour [up to 20 minutes following completion of the infusion] and 2 hours [± 20 minutes] after initiation of infusion)
- Anti-dystrophin antibody (predose)
- Anti-viltolarsen antibody (predose)
- PK blood sample (predose [within 60 minutes prior to infusion], 2 hours [± 20 minutes] after initiation of infusion, and 6 hours [± 20 minutes] after initiation of infusion)
- Patient reported outcomes
 - TSQM
- IP administration
- AE review
- Data upload from ActiGraph GT9x

10.3 End-of-Treatment Phase

10.3.1 Week 49

The following assessments will occur:

- Medical history (any updates will be recorded)
- Height and weight
- Vital signs
- Physical and neurological examination
- 12-lead ECG
- Renal ultrasound
- Echocardiogram
- Hematology
- Chemistry

- First morning void urinalysis
Note: Analysis of the first morning void urine sample will include urine dipstick protein to be performed at the site.
- Urine cytology (utilizing a urine sample collected on-site)
- Respiratory assessments
 - FVC
 - FEV1
 - PEF
 - PCF
- Function and strength
 - NSAA
 - Vignos scale
 - Hand-held dynamometer
 - Brooke scale
 - PUL
- Patient reported outcomes
 - PODCI
 - PARS III Questionnaire
- AE review
- Data upload from ActiGraph GT9x

10.3.2 Follow-up Phone Call

Patients will have a phone call conducted by a member of the site study staff, 30 days (± 3 days) following the last IP infusion, to assess AEs; actigraphy; and medical, surgical, medication, and treatment review. Any AE(s) that is unresolved will be followed up by the site (investigator or designee) for as long as medically indicated. The clinical research organization (CRO) retains the right to request additional information for any patient with ongoing AEs at the end of the study, if judged necessary.

10.3.3 Unscheduled Visit

If a patient returns to the clinic for a visit outside of the protocol evaluation time points, the visit and any assessments and/or tests performed will be recorded in the source documents and the eCRF as an Unscheduled Visit.

10.3.4 Early Termination or Withdrawal from the Study

A patient (or the legal guardian acting on behalf of the patient) is free to withdraw consent and discontinue participation in the study at any time, without prejudice to further treatment, according to standard clinical practice. Study participation may be discontinued at any time at the discretion of the investigator or sponsor. The following may be justifiable reasons for removing a patient:

- Withdrawal of consent by the patient/legal guardian
- Failure to comply with the protocol
- Lost-to-follow-up
- Illness, condition, or procedural complication (including AEs) affecting the patient's ability to participate or requiring prohibited medication
- In the investigator's judgment, it is deemed in the best interest of the patient to discontinue his/her participation in the study
- The investigator, sponsor, Data and Safety Monitoring Board (DSMB), and/or regulatory authority terminates the study
- Any other reason

A Patient Completion/Discontinuation eCRF, describing the reason for discontinuation, must be completed for any discontinued or withdrawn patient regardless of reason. If a patient withdraws from the study or if the study is prematurely terminated, the investigator or designee will contact the patient or the patient's legal guardian **within 30** days after withdrawal or termination to assess any AEs. The investigator will be asked to follow all SAEs until the event returns to baseline or until the investigator determines that follow-up is no longer medically necessary.

Patients who are withdrawn from the study may not re-enter.

The following assessments should be performed at the time of early termination:

- Medical history (any updates will be recorded)

- Height and weight
- Vital signs
- Physical and neurological examination
- 12-lead ECG
- Renal ultrasound
- Echocardiogram
- Hematology
- Chemistry
- First morning void urinalysis

Note: Analysis of the first morning void urine sample will include urine dipstick protein to be performed at the site.

- Urine cytology (utilizing a urine sample collected on-site)
- Respiratory assessments
 - FVC
 - FEV1
 - PEF
 - PCF
- Function and strength
 - NSAA
 - Vignos scale
 - Hand-held dynamometer
 - Brooke scale
 - PUL
- Patient reported outcomes
 - PODCI
 - PARS III Questionnaire
- AE review
- Data upload from ActiGraph GT9x

If a patient is lost to follow-up, every reasonable effort must be made by the clinical site personnel to contact the patient and determine the reason for discontinuation/withdrawal

(including assessment of any AEs reported by the patient/caregiver). The measures taken to follow-up must be documented in source documents.

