- s. To be performed on a predose urine sample collected on-site.
- t. To be performed on a urine sample collected within 5 hours after completion of infusion.
- u. To include hepatitis B antigen, hepatitis C antibody, and HIV antibody.
- v. To be collected predose and to be performed on serum blood samples.
- w. PK blood samples will be collected predose (within 60 minutes prior to infusion) and 2 hours (± 20 minutes) after initiation of infusion on Day 1 and at Week 13.
- x. Function and strength tests will include the following: Brooke and Vignos scales, PUL, NSAA, and hand-held dynamometer.
- y. PODCI and PARS III Questionnaire.
- z. ActiGraph GT9x will be provided at Screening; 10 hour daytime + full nighttime wear for full study period.
- aa. IP infusion will be administered every week within a ± 3 -day window. A minimum of 3 days (72 hours) should elapse between infusions.
- bb. The chest X-ray will include images of the heart, lungs, airways, blood vessels, and the bones of the spine and chest.

Table 2. Schedule of Study Assessments for Treatment Phase from Week 25 to End of Treatment Phase

Assessment ^a	Treatment Phase (Week 25 to Week 48) ^b ±3 days for each weekly visit														End-of-Treatment Phase		
	25	26 to 28	29	30 to 32	33	34 to 36	37	38 to 40	41	42 to 44	45	46	47	48	49	Follow-up Telephone Call ^c 30 days (±3 days) postdose	ET
General Procedures																	
Medical history ^d	X	X	X	X	X	X	X	X	X	X	X	X	X	X	X	X	X
Height ^e and weight ^f	X						X								X		X
Vital signs ^g	X	X	X	X	X	X	X	X	X	X	X	X	X	X	X		X
Physical and neurological examination ^h	X						X								X		X
12-lead ECG ⁱ	X						X								X		X
Renal ultrasound ^j	X														X		X
Echocardiogram ^k	X														X		X
Laboratory Assessments^l																	
Hematology ^m	X						X								X		X
Chemistry ^m	X						X								X		X
First morning void urinalysis ^{m,n}	X		X		X		X		X		X				X		X
Urine cytology ^o	X						X								X		X
Postdose urinalysis ^{m,p}	X						X										
Anti-dystrophin antibody ^q	X						X								X		
Anti-viltolarsen antibody ^q	X						X								X		
Pharmacokinetic Assessment																	
PK (blood) ^{l,r}	X						X								X		

Assessment ^a	Treatment Phase (Week 25 to Week 48) ^b ±3 days for each weekly visit														End-of-Treatment Phase		
	25	26 to 28	29	30 to 32	33	34 to 36	37	38 to 40	41	42 to 44	45	46	47	48	49	Follow-up Telephone Call ^c 30 days (±3 days) postdose	ET
Other Assessments																	

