3 STUDY OBJECTIVES AND ENDPOINTS

Primary Objective	Primary Endpoints

 To evaluate the safety and tolerability of viltolarsen administered IV at weekly doses of 80 mg/kg in ambulant and non-ambulant boys ≥ 8 years of age with DMD 	
 Vital signs Physical examination Renal ultrasound Echocardiogram Clinical laboratory tests 
 Hematology and clinical chemistry Urinalysis Urine cytology 12-lead electrocardiogram (ECG) Anti-viltolarsen antibodies Anti-dystrophin antibodies TEAEs and SAEs
Secondary Objective	Secondary Endpoints

 To compare the efficacy of viltolarsen administered IV at weekly doses of 80 mg/kg over a 48-week Treatment Period versus natural history controls in ambulant and non-ambulant boys ≥ 8 years of age with DMD 	
 Peak Expiratory Flow (PEF) Forced Vital Capacity (FVC) Forced expiratory volume in 1 second (FEV1) PUL Brooke scale Vignos scale Hand-held dynamometer NSAA
Exploratory Objectives	Exploratory Endpoints

 To evaluate health-related quality of life impact of viltolarsen treatment on patient's DMD 	
 Treatment Satisfaction Questionnaire (TSQM) Pediatric Outcome Data Collection Instrument (PODCI) Personal Adjustment and Role Skills Scale, 3rd edition (PARS III) Questionnaire

 To evaluate strength of cough in patients with DMD 	
 Peak Cough Flow (PCF)

 To evaluate preservation of ambulation of patients with DMD 	
 Loss of ambulation

 To evaluate daily activity and sleep-wake patterns to explore impact of viltolarsen treatment on patient's DMD 	
 Accelerometry measures of activity and sleep-wake patterns

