9.15.3 Anti-Viltolarsen Antibody

Anti-viltolarsen antibody testing will be performed on serum blood samples collected predose during the visits specified in the Schedules of Study Assessments (Table 1 and Table 2).

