10.3.5 Procedures for Early Termination

If a patient withdraws or is removed from the study for any reason, all early termination procedures should be completed per the Schedules of Study Assessments ([Table 1](#) and [Table 2](#)). Reason for withdrawal, date of the discontinuation, and date of the last dose of IP should be recorded in source documents and in the appropriate section of the eCRF. IP assigned to the withdrawn patient may not be assigned to another patient.

The medical monitor and study chair should be consulted prior to the withdrawal of the study patient, except in the case of a medical emergency. Written notice (regardless of cause) is to be provided to the medical monitor within 48 hours of the withdrawal. At the time of discontinuation, every effort should be made to ensure all relevant procedures and evaluations scheduled for the final study visit are performed. At the time of discontinuation, a self-addressed stamped shipper will be sent to the patient for returning of the ActiGraph GT9x and all accessories.

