10.4 Patient Replacement

Patients will not be replaced.

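### Both antibodies are primary endpoints, but the protocol requires no antibody sample at early termination, so a boy who stops before Week 13 has no required on-treatment result.

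*Combined protocol and SAP*

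**What the plan says.** Section 3 places the antibodies in the primary endpoint cell, which ends "Anti-viltolarsen antibodies Anti-dystrophin antibodies TEAEs and SAEs". Section 9.15.3 sets their timing: "Anti-viltolarsen antibody testing will be performed on serum blood samples collected predose during the visits specified in the Schedules of Study Assessments". Section 9.15.2 says the same for anti-dystrophin antibody.

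For boys who leave early, Section 10.3.4 opens its list with "The following assessments should be performed at the time of early termination". The list includes ECG, renal ultrasound, echocardiogram, hematology, chemistry, first morning void urinalysis, urine cytology, respiratory and function tests, and questionnaires. It contains no antibody sample. Section 10.3.5 says that "all early termination procedures should be completed per the Schedules of Study Assessments". Only Table 2 has an ET column. That column is marked for hematology, chemistry and urine cytology, and blank for both antibodies.

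Section 10.3.5 adds that "every effort should be made to ensure all relevant procedures and evaluations scheduled for the final study visit are performed". The Week 49 list in Section 10.3.1 has no antibody sample.

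The reasons for removal in Section 10.3.4 include "Illness, condition, or procedural complication (including AEs) affecting the patient's ability to participate or requiring prohibited medication". Section 10.4 states "Patients will not be replaced". Section 12.7.1.1 plans a summary of antibodies over time. Section 12.9 makes no imputation the default.

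**The concern.** The ET visit repeats almost every primary safety measure except these two. Blood is already being drawn there, and the protocol gives no reason for leaving the antibodies out.

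Antibody visits are about 12 weeks apart, so a boy who stops will usually do so between them. Section 5.2.4 foresees acute reactions during infusion, and adverse events are a listed reason for removal. For a boy who leaves after such a reaction, an antibody result is of particular interest, yet none is required. In a single-arm trial of 20 whose primary objective is safety, a gap in a primary safety measure that may be related to why boys stop deserves closing.

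**Working it through.** **1. Is the omission consistent across the documents?**

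| Place | Antibody sample at ET? |
|---|---|
| Section 10.3.4 list | Not listed |
| Table 2, ET column | Blank in both antibody rows; marked for hematology, chemistry, cytology |
| Section 10.3.5, first paragraph | Refers back to Tables 1 and 2 |
| Section 10.3.5, final-visit sentence | Best effort only; the Week 49 list in 10.3.1 has none |
| Sections 10.3.3 and 11.10 | Unscheduled or investigator-chosen tests possible; antibodies not named |

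Text and table agree, so a PDF reading error is an unlikely explanation.

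**2. How old can the last required sample be?** The visit lists in Sections 10.2.1, 10.2.9, 10.2.15, 10.2.17 and 10.2.19 put antibody samples at Day 1 (Week 1) and Weeks 13, 25, 37 and 48. All are predose. With weekly dosing, the largest number of infusions between a sample and the next one is the next week number minus the last.

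| Last sample | Next sample | Infusions possible in between |
|---|---|---|
| Week 1 | Week 13 | 13 − 1 = 12 (Weeks 1 to 12) |
| Week 13 | Week 25 | 25 − 13 = 12 (Weeks 13 to 24) |
| Week 25 | Week 37 | 37 − 25 = 12 (Weeks 25 to 36) |
| Week 37 | Week 48 | 48 − 37 = 11 (Weeks 37 to 47) |

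In the first row the only required sample precedes the first dose, so there is no on-treatment result. In the later rows an earlier on-treatment result exists, but it may be up to 12 infusions old.

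**3. Where is the last scheduled sample?** Section 10.2.19 says Week 48. In Table 2, as read from the PDF, the last antibody mark falls under Week 49. The PK row is marked the same way, yet its footnote r says Week 48, and the blood-volume text in Section 9.15.1 lists Week 48 as a draw day. The mark may therefore be a shifted column or a real mismatch. If Week 49 were right, the last gap would be 49 − 37 = 12 infusions, so the maximum stays at 12.

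**4. What does one boy weigh?** 1/20 = 5% of the planned sample.

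**5. The plan's own detection figure.** Section 12.2 gives at least 95% probability of seeing one or more adverse drug reactions of 15% incidence in 20 patients. Check: 1 − 0.85^20 = 0.9612, which agrees.

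As an illustration only, assume a 15% antibody incidence and let n be the number of boys with a post-dose antibody result.

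| n | 1 − 0.85^n |
|---|---|
| 20 | 0.9612 |
| 19 | 0.9544 |
| 18 | 0.9464 |
| 17 | 0.9369 |

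The 95% level needs n ≥ ln(0.05)/ln(0.85) = 18.43, so 19 boys. Two boys without a post-dose result would take this endpoint just below it. The 15% is borrowed from a statement about adverse drug reactions; the documents give no expected antibody incidence.

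**The case against.** The strongest objection is that the protocol already leaves room for the test. Section 11.10 requires relevant laboratory tests to be repeated after an adverse event that forces discontinuation, and Section 10.3.3 records any unscheduled test. If the Week 49 mark in Table 2 is real, the final-visit sentence in Section 10.3.5 could also reach the antibodies. This stands in part: a sample can be taken. But nothing requires one, the choice rests with each site, and reading the final-visit sentence that way would conflict with the blank ET cell.

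The event may also be rare. Section 2.3.3 reports no antibodies in the Phase 1/2 study at 40 or 80 mg/kg, and no discontinuation of study drug for an adverse event in that study or in Studies 201 and 202. That limits the weight of the point but does not remove it. The remedy costs something only when a boy actually stops.

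A reader might infer three stronger claims that the documents do not support.

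- **That an immune cause could never be confirmed or excluded.** Discretionary testing is available, earlier results remain, and a boy who stops at an antibody visit may have a current result.
- **That antibody incidence is biased downward.** This holds only if stopping is related to an immune reaction. Section 12.7.1.1 plans a summary over time and defines no incidence or denominator.
- **That drug-level information is also lost because Section 9.17.1 ties the plasma assay to antibody detection.** ET is not a dosing visit in Table 2 and has no PK draw, and an antibody tube would not supply one. The human half-life in Section 2.3.3 is 1.52 to 1.84 hours, measured at doses up to 20 mg/kg. Assuming ET falls at least 72 hours after the last dose (the minimum spacing between infusions), 72/1.84 ≈ 39 half-lives would have passed, leaving essentially nothing to measure. Samples already drawn at scheduled visits are unaffected.

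**Conclusion.** The gap is real and modest. Two primary endpoints have no required sample at early termination, and no other clause makes one mandatory. A boy who stops before Week 13 has no required on-treatment antibody result after up to 12 infusions; one who stops later may have had up to 12 since his last sample. Each boy without a post-dose result is 5% of a sample that is not topped up.

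The infusion counts rest on the visit text being the intended schedule and on no missed doses. Understatement of antibody positivity is conditional on stopping being related to an immune reaction, and the protocol gives no expected number of such withdrawals. This is a low-cost improvement to a primary safety measure, not a defect that undermines the trial.

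**What to change.** - Add anti-viltolarsen and anti-dystrophin antibody serum to the list in Section 10.3.4 and to the ET column of Table 2.
- Adapt footnote q of Table 2, since a predose sample has no meaning at a visit without dosing.
- In the SAP, report ever-positive incidence for each antibody with ET samples included, among boys with at least one post-dose result, and state how many boys have none.
- Reconcile the last scheduled antibody time point between Section 10.2.19 (Week 48) and Table 2 (apparently Week 49).

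The cost is about one extra serum tube, at a visit where hematology and chemistry blood is already drawn, in the few boys who stop early. The blood-volume text in Section 9.15.1 and the laboratory manual need a small update. The sample size does not change.
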